9 STATISTICAL CONSIDERATIONS

9.1 STATISTICAL HYPOTHESES

Primary Efficacy Endpoint(s):

- H1 (Objective 1): There will be an improvement in the oral hygiene clinical outcomes (lower plaque index and lower gingival index) from baseline to Month 3 and Month 6, and from Month 3 to Month 6. Treatment Group 1 will have a higher rate of improvement than the control group while Treatment Group 2 will have the highest rate of improvement.
- H2b (Objective 2b): The effects of the intervention on oral hygiene clinical outcomes (i.e., plaque index and gingival index) will be mediated by a set of mediating variables controlling for selected key covariates.
- H3a (Objective 3a): The effects of the intervention on oral hygiene clinical outcomes (i.e., plaque index and gingival index) will be mediated by oral hygiene behavioral outcomes controlling for selected key covariates.
- H3b (Objective 3b): The effects of the intervention on oral hygiene clinical outcomes (i.e., plaque index and gingival index) will be mediated by care partner's factors, and then mediated by oral hygiene behavioral outcomes controlling for selected key covariates.

Secondary Efficacy Endpoint(s):

- H1 (Objective 1): There will be an improvement in the oral hygiene behaviors (better oral hygiene skills and higher frequency of toothbrushing) from baseline to Month 3 and Month 6, and from Month 3 to Month 6. Treatment Group 1 will have a higher rate of improvement than the control group while Treatment Group 2 will have the highest rate of improvement.
- H1 (Objective 1): There will be an improvement in the oral hygiene behaviors (longer duration of toothbrushing) from the first week of the intervention (average in Week 1) to Month 3 (average in Month 3) and Month 6 (average in Month 6), and from Month 3 to Month 6. Treatment Group 2 will have longer duration of toothbrushing than the Treatment Group 1.
- H2a (Objective 2a): The effects of the intervention on oral hygiene behavioral outcomes (i.e., the duration and frequency of toothbrushing and oral hygiene skills) will be mediated by a set of mediating variables controlling for selected key covariates.

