9.4 STATISTICAL ANALYSES

9.4.1 GENERAL APPROACH

A statistical analysis plan (SAP) will be prepared and finalized prior to database lock and unblinding of participant's treatment assignment. This document will provide further details regarding the definition of analysis variables and analysis methodology to address all study objectives. A blinded data review will be conducted prior to unblinding of the participants' treatment assignments. This review will assess the accuracy and completeness of the study database, participant evalability, and appropriateness of the planned statistical methods. The SAP will not be posted publicly or registered before the study begins.

We will conduct data analysis in the following steps:

- Descriptive analysis on the sample characteristics, potential mediators, and oral hygiene behavioral and clinical outcomes. For the categorical variables, we will present percentages. For continuous variables, we will present means (with range and standard deviations).
- We will conduct ANOVA and Chi-Square analysis to compare group differences for the variables listed above. This will be based on two-tailed hypothesis testing. We will use p-value and 95% confidence interval for statistical significance test. P value of 0.05 will be considered the level of significance.
- We will use linear mixed models for continuous outcomes (e.g., plaque index, gingival index, oral hygiene skills, and duration of toothbrushing from smart toothbrush) accounting for within-participant correlation over time.
- We will use generalized linear mixed models for ordinal variables (e.g., self-reported duration of toothbrushing) accounting for within-participant correlation over time.
- Key covariates will be specified in the SAP.
- The tests for the underlying assumptions for the models will be specified in the SAP.

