General Approach: The overall goal of this study is to demonstrate the effectiveness of the two intervention strategies (TG1, TG2) against that of CG. The primary outcomes are plaque index, which is quantified as the proportion of sites with plaque deposits on at least less than 1/3 of crown, and gingival index, which is quantified as the proportion of sites with at least some mild inflammation. While the unit of randomization is at the dyad level, the primary outcomes will be evaluated at the individual level. As participants and care-partners contribute repeated measures (at baseline, 3 months and 6 months), we will use a linear mixed modeling approach for the analysis of the primary hypotheses, to account for correlation among repeated measures from the same individual. Analyses for all study outcomes will be conducted according to the intention-to-treat (ITT) principle, where all participants are analyzed according to the group in which they were randomized, irrespective of their receipt of allocated treatment. For our primary analysis we will conduct a

complete case analysis, thus excluding participants who are lost to follow up. As a sensitivity analysis, we will use the strategy of last-observation-carried-forward (LOCF) (thus assuming no change), to impute missing values for participants lost to follow up, if a monotone pattern is demonstrated in complete data. A strategy of LOCF is conservative in that it may bias results towards a null effect, but eliminates bias related to differential dropout, especially in the case where participants with no improvement are less likely to complete follow-up assessments. Statistical analyses will be performed in R version 4.4.0. All statistical tests will be two-sided, and a p-value of < 0.05 will be considered statistically significant.

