Statistical Analyses (Aim 1): To examine between-group differences in baseline characteristics and outcome variables, we will use Chi-square tests or Fisher's exact tests to analyze categorical variables and a one-way analysis of variance (ANOVA) for continuous variables. The effectiveness hypotheses will be analyzed using a linear mixed modeling framework with random effects. Specifically, longitudinal outcomes (e.g. plaque index) will be regressed on a treatment indicator, timepoint indicator, interaction of the two, and additional participant-specific covariates as needed. That is for the i^{th} person and t timepoint, $\text{Plaque}_{it} = \alpha_i + \beta_0 + \beta_1 \cdot \text{Site}_i + \beta_2 \cdot X_i + \beta_g \cdot \text{Group}_i + \beta_t \cdot \text{Time}_t + \beta_{gt} \cdot \text{Group}_i \times \text{Time}_t + \varepsilon_{it}$, where the terms represent the following: α_i person-specific random effects, β_0 overall mean plaque, β_1 site effects, X_i additional participant-specific covariates, β_g group effects, β_t time effects, and β_{gt} the interaction effect between group and time. Covariates determined a priori (including: baseline index scores, baseline functional status) will be included via the flexible X_i term. If data suggest a between-group difference (e.g. significant interaction between time and group) on the primary outcomes of interest, we will conduct the following pairwise comparisons using estimated means (**TG1 vs. CG**; **TG2 vs. CG**), at 3 months and 6 months. To control for multiple comparisons, pairwise comparisons will incorporate a False Discovery Rate-controlling procedure (e.g. Benjamini-Hochberg) which yields the desired type-I error rate of 5%. Lastly, depending on the distribution of the proportions for the primary outcomes (plaque, gingival indices) we may explore alternative distributions (e.g. beta regression) if it improves model fit. To address secondary outcomes including: 1) participants' frequency of toothbrushing, 2) participant's duration of toothbrushing, 3) participants frequency of interdental cleaning, 4) participant's interproximal cleaning technique, and 5) participants' oral hygiene skills score, and 6) participants' oral health knowledge score, we will use the same analytic approach outlined above consisting of linear mixed modeling with random effects. Given the overall sample size and number of secondary outcomes, all secondary outcome analyses will incorporate an appropriate False Discovery Rate-controlling procedure (e.g. Benjamini-Hochberg).

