
Exploratory Analyses (Aim 2): If findings from the analyses outlined above, for the primary outcomes of plaque and gingival indices, indicate an overall intervention effect, we will consider exploratory mediation analysis. Specifically, if a significant effect of the two treatment packages is observed (relative to control), we will explore the extent to which the proposed mediators (oral care self-efficacy, leadership self-efficacy, use of behaviors-cueing, or leadership communication) mediate the effect of the two treatment packages compared to control on the primary outcomes (plaque and gingival indices). Given the available sample size, we will consider the mediators independently and estimate preliminary single mediation effects using causal mediation analysis. Model-based causal mediation involves a two-step process. First, we specify a mediator model to obtain the conditional distribution of the mediator given the exposure, and an outcome model to obtain the conditional distribution of the outcome given the exposure and mediator. Each model is fit separately and then their fitted objects are inputted into a mediation function, which estimates the effects of interest. The mediator model will be specified as a linear regression of the mediator at 3 months post-randomization on the exposure (treatment allocation) and baseline values of the mediator. The outcome model will be specified as a linear regression of the outcome at 6 months post-randomization on the mediator at baseline, and 3 months after randomization, and the exposure (randomization assignment). Using the mediator and outcome regression models we will estimate the corresponding preliminary indirect and direct effects for each mediator. Of particular interest to the present study are the preliminary indirect effect estimates, which measure the effect of the exposure (randomization assignment) on the outcome (plaque or gingival index) via the mediator of interest (e.g. oral care self-efficacy). We will estimate corresponding standard errors and 95% confidence intervals for these effects using bootstrapping.

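### The exploratory mediation outcome model omits the baseline plaque or gingival index; this costs precision and can bias the indirect effect, in a direction the documents do not settle

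*Combined protocol and SAP*

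**What the plan says.** The SAP (Exploratory Analyses, Aim 2) writes out both mediation models. The mediator model is a "linear regression of the mediator at 3 months post-randomization on the exposure (treatment allocation) and baseline values of the mediator". The outcome model is a "linear regression of the outcome at 6 months post-randomization on the mediator at baseline, and 3 months after randomization", with arm as the only other regressor. Neither has the baseline plaque or gingival index, site, or an open covariate term.

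The Aim 1 model in the same SAP is different. It has a site term and states: "Covariates determined a priori (including: baseline index scores, baseline functional status) will be included via the flexible X_i term". The baseline index is available for every arm. The SAP's General Approach says: "As participants and care-partners contribute repeated measures (at baseline, 3 months and 6 months"), and the baseline column of the protocol's Schedule of Activities (section 1.3) has an oral health evaluation in all three groups.

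The protocol also expects covariates in the mediation analysis. Section 9.1 says that the effects "will be mediated by a set of mediating variables controlling for selected key covariates", and section 9.4.1 adds: "Key covariates will be specified in the SAP". The SAP names covariates for Aim 1 but none for mediation.

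**The concern.** Randomisation protects the comparison of arms on the mediator. It does not protect the step from the mediator to the outcome, because dyads with high and low 3-month self-efficacy, cueing or communication scores were not formed by chance. That step relies on covariate adjustment, and the earlier value of the outcome is the first candidate. Adjusting for the baseline mediator does not replace it.

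There is a plausible route from baseline oral status to the later mediator. Protocol section 6.1.1 has the hygienist go through the examination findings with the participant and care partner in Treatment Group 2. A poor baseline examination could prompt more cueing or lower confidence. If so, part of the estimated indirect effect would reflect where the participant started rather than what the mediator did.

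Precision is also at stake. Only 54 participants had completed at the SAP's count of 05/08/24, and the SAP falls back to descriptive summaries if intervals are wide. A covariate that narrows them for almost no cost is worth having.

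**Working it through.** The SAP states no figure to reproduce. The check is omitted-variable algebra for the planned models, confirmed by simulation.

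**Set-up (SD units, linear, no arm-by-mediator interaction)**
- a: effect of arm on the 3-month mediator
- g: effect of the baseline index on the 3-month mediator, given arm and baseline mediator
- d: effect of the baseline index on the 6-month index
- r: baseline correlation between mediator and index
- v: residual variance of the 3-month mediator

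Bias of the indirect effect = a × d × δ, where δ = g(1 − r²) / [g²(1 − r²) + v].

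**Inputs.** From the documents: the two model specifications and the completer counts (18, 17 and 19, total 54). Everything else is assumed because the documents give no values: a = 0.8, mediator stability 0.5 (so v = 1 − 0.25 = 0.75), d = 0.4 to 0.7, r = −0.2 to −0.5, and no true mediation.

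**Result 1: g = 0.** Then δ = 0 and the bias is zero whatever r and d are. A baseline correlation between mediator and index is not enough, because the planned model already holds the baseline mediator fixed. Simulation agrees, at 0.000 to 0.001 SD.

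**Result 2: g of size 0.15.**
- r = −0.2: δ = 0.15 × 0.96 / (0.0225 × 0.96 + 0.75) = 0.144 / 0.7716 = 0.187
- r = −0.5: δ = 0.1125 / 0.7669 = 0.147
- Smallest bias: 0.8 × 0.4 × 0.147 = 0.047. Largest: 0.8 × 0.7 × 0.187 = 0.105.

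**Result 3: g of size 0.3.**
- r = −0.2: δ = 0.288 / 0.8364 = 0.344
- r = −0.5: δ = 0.225 / 0.8175 = 0.275
- Smallest bias: 0.8 × 0.4 × 0.275 = 0.088. Largest: 0.8 × 0.7 × 0.344 = 0.193.

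**Direction.** The bias takes the sign of g. A separate set of runs used a true indirect effect of 0.8 × (−0.3) = −0.24 (negative means a lower index), d = 0.3 to 0.6, r = 0 or −0.3, and mediator residual SD 0.75.

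| g | Planned model estimates | Baseline index added |
|---|---|---|
| 0 | about −0.24 | about −0.24 |
| −0.3 | −0.34 to −0.46 | about −0.24 |
| +0.3 | −0.14 to −0.02 | about −0.24 |

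So the planned model can exaggerate mediation or hide it. The last column recovers the truth by construction, since the baseline index is the only confounder in the simulation.

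**Precision with no confounding (g = 0), n = 54, d = 0.6.** The SE of the mediator path is roughly the residual SD of the outcome divided by √(v × residual degrees of freedom of the mediator).
- Without the baseline index, the residual SD is √(1 − 0.36r²), or 0.993 at r = −0.2 and 0.954 at r = −0.5. SE ≈ 0.993 / √(0.75 × 51) = 0.16 and 0.954 / 6.18 = 0.15.
- With it, the residual SD is √(1 − 0.36) = 0.80. SE ≈ 0.80 / √(0.75 × 50) = 0.13.
- Simulation gives about 0.16 and 0.13.

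For Treatment Group 2 against control alone (17 + 19 = 36 completers; true indirect effect −0.24, d = 0.6, r = −0.3, g = 0), the simulated SD of the indirect effect falls from 0.20 to 0.16.

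**The case against.** The strongest reply is that bias is possible but not shown. The planned model already includes the baseline mediator, which blocks any confounding that runs only through the baseline association of mediator and index. Bias needs a further link from the baseline index to the 3-month mediator, and the documents give no figure for it. This stands. A reader might infer that the planned analysis will show mediation where there is none. The documents do not support that: the bias may be zero, and a positive link would shrink a real indirect effect instead.

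A second reply is that little depends on this model. The SAP treats the analysis as exploratory, runs it only after a significant primary effect, calls its estimates preliminary, and has a descriptive fallback. This also stands. A reader might infer that a biased indirect effect would feed the design of a later trial. The SAP ties that purpose to the fallback summaries of mean change and Cohen's d, which do not use this outcome model.

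A third reply is that the mediator model needs no baseline index to remove bias, because arm is randomised, and that nothing in the documents shows site to be a confounder. Both points are correct. The case for those additions is consistency and precision.

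None of this answers the omission itself. The index is collected, Aim 1 adjusts for it, and the protocol left the mediation covariates for the SAP to name.

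**Conclusion.** The concern holds in a limited form. The outcome model leaves out a collected baseline value that Aim 1 treats as an a priori covariate, and the protocol's undertaking to control for key covariates is unmet for mediation. The omission can bias the indirect effect in either direction: zero if the baseline index does not predict the 3-month mediator given arm and baseline mediator, about 0.05 to 0.10 SD if that link is 0.15, and about 0.09 to 0.19 SD if it is 0.3. These sizes rest on the assumed values listed above, not on trial data.

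The loss of precision does not depend on that link. It needs only that the baseline index predicts the 6-month index, which is likely. At an assumed correlation of 0.6 and n = 54, the standard error is about 0.16 rather than 0.13.

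No primary or secondary conclusion is affected. This is a change to consider, held with medium confidence.

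**What to change.** In the SAP's Aim 2 section, add the baseline value of the same index (plaque for plaque, gingival for gingival) to the outcome model. Use the same covariate in the mediator model for consistency and precision. Site, the stratification factor already in the Aim 1 model, can be added to both. State that these are the key covariates that protocol section 9.4.1 leaves to the SAP.

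The cost is SAP wording and about two degrees of freedom per model (one for the index, one for two sites). No new data are needed. Because the baseline index may not be the only common cause of mediator and outcome, a short sensitivity analysis for unmeasured mediator-outcome confounding would be a useful optional addition.

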Should model diagnostics from our exploratory mediation analysis (e.g. RMSEA) indicate poor model fit or we observe indications of instability in effect estimates (e.g. wide confidence intervals), we will opt for a paired down assessment of potential mediators. In this paired down approach, we will explore changes in potential mediators following intervention (e.g. oral care self-efficacy) by summarizing mean change (6 months - baseline), (3 months - baseline) in potential mediators stratified by intervention group (**TG1, TG2, CG**). To inform future studies, we will calculate corresponding effect sizes (Cohen's d for independent samples) for key between-group differences (**TG1 vs. CG; TG2 vs. CG**) in mean change for potential mediators (e.g. oral care self-efficacy). These descriptive summaries will provide inputs to aid in powering a future mediation analysis to examine the underlying mechanisms of intervention effects.

Supplementary Strategies

Assessment of Modified Measures. For modified scales, which include the secondary outcome of oral care self-efficacy, and the exploratory mediators of adaptive leadership and focused communication, we will confirm unidimensionality via exploratory factor analysis, and subsequently compute Cronbach's alpha to examine reliability for each modified scale.

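### The Aim 2 mediation fallback names a fit index its models cannot produce, switches on undefined interval width, and is the only planned route to between-arm effect sizes for the mediators

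*Combined protocol and SAP*

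**What the plan says.** All of this is in the SAP, Exploratory Analyses (Aim 2), unless another place is named.

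- **Entry condition.** Mediation is explored "if a significant effect of the two treatment packages is observed (relative to control").
- **Method.** Given the sample available, "we will consider the mediators independently and estimate preliminary single mediation effects using causal mediation analysis". On estimation: "Each model is fit separately and then their fitted objects are inputted into a mediation function, which estimates the effects of interest".
- **Models.** The mediator model is a "linear regression of the mediator at 3 months post-randomization on the exposure (treatment allocation) and baseline values of the mediator". The outcome model is a "linear regression of the outcome at 6 months post-randomization on the mediator at baseline, and 3 months after randomization, and the exposure (randomization assignment"). Standard errors and 95% intervals come from the bootstrap.
- **Fallback, first trigger.** "Should model diagnostics from our exploratory mediation analysis (e.g. RMSEA) indicate poor model fit".
- **Fallback, second trigger and consequence.** The team also switches if it sees unstable estimates ("e.g. wide confidence intervals), we will opt for a paired down assessment of potential mediators"). The reduced assessment is mean change in each mediator (3 and 6 months minus baseline) by arm, with Cohen's d for TG1 vs CG and TG2 vs CG, meant to help power a later study.
- **Stated purpose.** Under Study Aims, Aim 2 is to assess how the mediating and process factors change.
- **Unconditional output.** Under Descriptive Tables, Table 4 gives the four mediators by arm at each visit, and Table 6 gives the cueing items.

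**The concern.** A fallback rule is useful only if it can be evaluated and does not depend on how the result looks. Here the one fit index named belongs to over-identified covariance-structure models, not to a pair of ordinary regressions. The one sign of instability named, a wide interval, has no numerical limit or scale. The SAP does not say who decides, or whether the switch applies to one mediator or to all four.

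The order of analyses raises a second problem. Whether the intervention moved its mediators can be answered whatever happens to plaque and gingival index, and needs no mediation model. Yet the between-arm effect sizes for mediator change sit at the end of a chain: significant primary result, then mediation attempted, then mediation judged unsatisfactory. What is at stake is the mechanism evidence this trial can pass to a later study.

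**Working it through.** The plan states no figure on this point, so the check covers model structure, a simulation and the branches of the plan.

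**1. Can RMSEA exist for these models?** Write the two regressions as one path model. The exogenous variables are exposure and baseline mediator; the endogenous variables are the 3-month mediator and 6-month outcome. With p observed variables there are p(p+1)/2 moments.

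| | One exposure dummy | Two exposure dummies |
|---|---|---|
| Observed variables p | 4 | 5 |
| Moments p(p+1)/2 | 10 | 15 |
| Exogenous variances and covariances | 3 | 6 |
| Paths (mediator + outcome model) | 2 + 3 = 5 | 3 + 4 = 7 |
| Residual variances | 2 | 2 |
| Parameters | 10 | 15 |
| Degrees of freedom | 0 | 0 |

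RMSEA = √[max(0, χ² − df) / (df × (N − 1))]. With df = 0 the model reproduces the moments exactly and the expression is 0/0: undefined, or set to 0 by convention. It cannot indicate poor fit. The separately fitted regressions give no RMSEA at all.

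**2. Why width tracks the estimate.** The indirect effect is the product a×b, where a is exposure to mediator and b is mediator to outcome. To first order, SE² ≈ a²·SE(b)² + b²·SE(a)². Larger estimated paths therefore widen the interval, and selecting on width selects on the estimate.

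**3. Size of that selection.** From the documents: 17 TG2 and 19 CG completers (SAP sample size table) and the two SAP regressions. Assumed: a = 0.5 SD, b = 0.3, baseline-to-3-month mediator correlation 0.5, no direct effect, and a Monte Carlo 95% interval in place of the bootstrap. There were 3,000 simulated trials per scenario.

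| | a = 0.5 | a = 0.8 | a = 0 |
|---|---|---|---|
| True indirect effect | 0.15 | 0.24 | 0 |
| Median interval width | 0.60 | 0.76 | 0.48 |
| Correlation of width with absolute estimate | 0.79 | 0.66 | 0.67 |
| Mean estimate, narrower half | 0.07 | 0.14 | 0.00 |
| Mean estimate, wider half | 0.24 | 0.33 | 0.01 |
| 95% interval coverage, narrower half | 91% | 91% | 100% |

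With a = 0.5, the chance that a result counts as narrow enough is 3%, 29%, 82% or 96% if wide means above 0.3, 0.5, 0.8 or 1.0. An unstated limit thus leaves the decision almost entirely open. When the mediator is not moved (a = 0), selection on width causes no material bias; the shrinkage appears when there is an effect to find.

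**4. What each branch of the plan delivers for the four mediators.**

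| Primary result | Mediation judged | Planned beyond Tables 4 and 6 |
|---|---|---|
| Not significant | Not run | Nothing |
| Significant | Satisfactory | Mediation estimates; no change summaries or Cohen's d |
| Significant | Poor fit or unstable | Change summaries and Cohen's d; fate of the mediation estimates not stated |

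Only the last branch yields a between-arm effect size for mediator change.

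**The case against.** The best defence is that Aim 2 is labelled exploratory, its estimates are called preliminary, and no primary or secondary inference depends on it. That stands, and it keeps the point minor. Four stronger readings should also be resisted.

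- **That mediation results will be suppressed.** A reader might infer this from the switch. The SAP says only that the team will opt for the reduced assessment. It does not say that estimates already obtained go unreported, nor that they are reported. The simulated contrast shows what would follow if only narrow-interval results were kept; it does not describe a stated intention.
- **That interval width is the only trigger left.** RMSEA and wide intervals are both introduced as examples, so residual diagnostics or erratic bootstrap behaviour could also count. But no other criterion is named and none has a threshold.
- **That nothing on mediators is reported after a null primary result.** Tables 4 and 6 are unconditional. Oral health knowledge, which Aim 2 also names, is a secondary outcome and is modelled between arms anyway. What is missing for the four listed mediators is the change summary, the effect size and its interval.
- **That Aim 2 loses its effect sizes in about half of trials.** A three-arm one-way ANOVA with f = 0.3, N = 54 and alpha 0.05 has 46.8% power, but this is not the planned test. The SAP uses a covariate-adjusted mixed model with a group-by-time interaction on two primary outcomes, and protocol Section 9.2 does not identify its 0.3 as f. If the outcomes were independent, the figure would be 0.468² = 22% if both must be significant and 1 − 0.532² = 72% if either suffices; adjustment would move it again. The SAP does not say which applies, so no single figure is supportable.

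A sensitivity analysis for mediator-outcome confounding may be good practice, but it does not address this rule and is not part of the point.

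**Conclusion.** The point holds as a minor correction to a stated rule. That RMSEA cannot work here follows from the model specification and needs no assumption. That the width criterion is undefined and applied after the estimates are seen is plain from the text. How far it could mislead depends on assumed paths and on only narrow-interval results being kept. Under those assumptions, kept results average about half the true indirect effect (0.07 against 0.15) with coverage of 91%; with a larger mediator effect they average 0.14 against 0.24. The conditional placement of the mediator effect sizes also follows from the text, and sits badly with an aim worded around change in mediators. The consequence is limited to exploratory reporting on mechanism.

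**What to change.** In the SAP, Exploratory Analyses (Aim 2):

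1. Delete RMSEA and the interval-width switch.
2. Always report mean change in each mediator by arm (3 and 6 months minus baseline), with TG1 vs CG and TG2 vs CG effect sizes and 95% intervals, whatever the primary result.
3. Whenever mediation models are fitted, report the direct and indirect effects with bootstrap intervals whatever their width, alongside ordinary residual checks for both regressions. Imprecision is then shown by the interval, and the change summaries supplement the mediation results instead of replacing them.

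The cost is a few sentences of SAP wording and one extra table. No new data are needed.
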